There is increased infiltration of regulatory T (Treg) cells in the setting of both ischemic infarct and intracerebral hemorrhage. These cells are known for their anti-inflammatory function by mediating immune tolerance to self-antigens. Treg cells have been shown to decrease ICH-induced inflammatory injury.⁴¹ In a rat ICH model, Treg transfusion resulted in the inhibition of IL-1 β , TNF- α , and MMP-2 in the perihematomal tissue and increased presence of anti-inflammatory cytokines IL-4, IL-10, and TGF- β .⁴⁸ Treg cells have also been known to decrease perihematomal edema and BBB permeability after ICH, leading to improved short-term and long-term neurologic function in the animal model.⁴⁹

Table 3. T lymphocyte phenotype and functions

Phenotype	Molecule	Type	Role
Th1	IL-12, TNF- α	Cytokine	Activate macrophages and are responsible for cell-mediated immunity and phagocyte-dependent protective responses
	T-bet	Transcription factor	Induce Th1 phenotype, enhances production of IFN- γ and mediates repression of IL-4 expression
	STAT1	Transcription factor	Primarily regulates T-bet and mediates IL-4 repression to mediate Th1 cell commitment
Th2	IL-4, IL-5, IL-10, IL-13	Cytokines	Responsible for strong antibody production, eosinophil activation, and inhibition of several macrophage functions, providing phagocyte-independent protective responses
	GATA3	Transcription factor	Key for Th2 cytokine production; inhibition of Th1 responses
	STAT3	Transcription factor	Required by STAT6 for interaction with appropriate gene loci
	STAT5	Transcription factor	Independent of IL-4 signaling; coordinates with GATA3 to induce Th2 phenotype
	STAT6	Transcription factor	Upregulates expression of GATA3 and mediates Th2 cell phenotype
Th17	IL-17A/F, IL-21, IL22, IL-23, TGF- β	Cytokines	Creates inflammation and tissue injury in autoimmune diseases; unclear of function in ICH
	ROR γ t	Transcription factor	Master regulator to induce Th17 phenotype via STAT3 activation
	STAT3	Transcription factor	Activated by IL-6 and IL-23 to induce expression of ROR γ t

Treg	IL-2, IL-10, TGF- β	Cytokines	Essential for the maintenance of peripheral tolerance, prevention of autoimmune disease, and limiting chronic inflammatory disease
Foxp3	Transcription factor	Major lineage-specific transcription factor involved in Treg differentiation	
STAT5	Transcription factor	Enhances Foxp3 expression to promote Treg development	

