1.4 Sphingosine 1-Phosphate Receptor Modulation

Fingolimod (FTY720) is an oral immunomodulatory agent approved by the Food and Drug administration in 2010 for the treatment of relapsing-remitting multiple sclerosis (MS). It has been shown to reduce the number of MS relapses and limits the loss of brain volume via several mechanisms.⁵⁰⁻⁵² FTY720 is a functional analogue of phosphorylated sphingosine, a bioactive sphingolipid. In nature, sphingosine is phosphorylated by sphingosine kinase 1/2 (Sphk) to sphingosine 1-phosphate (S1P), which then binds to G-protein coupled receptors called sphingosine 1-phosphate receptors (S1PRs). There are five known S1PR subtypes, S1PR₁₋₅. S1PR₁₋₃ are broadly expressed in the immune and cardiovascular systems and the CNS. S1PR₁ is highly expressed on T and B lymphocytes. S1PR₄ is generally found in the hematopoietic and lymphoid tissues. S1PR₅ is predominantly found within the CNS white matter.⁵³ These receptors participate in a wide variety of biologic processes, including leukocyte recirculation, cellular proliferation and differentiation, morphologic changes, cellular motility, endothelial cell function, vascular regulation, and cardiovascular and nervous system development.⁵⁴ S1P and S1PRs play a key role in the maintenance of normal immune function. Once an appropriate activating antigen is encountered in the lymph nodes, naïve T cells become activated and enter the circulation to reach the corresponding site of inflammation.

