FTY720 is a sphingosine 1-phosphate receptor (S1PR) modulator and functions to regulate various cellular responses, including proliferation, apoptosis, and inflammation.⁵³ FTY720 binds with a high affinity to the following S1PR subtypes: S1PR₁, S1PR₃, S1PR₄, and S1PR₅.⁵³ As noted above, S1PR₁ is present on lymphocytes to aid in the egress of T cells with the appropriate antigen stimulation. The classic mechanism of action of FTY720 is presumed to be hematopoietic. Although structurally similarly to S1P, FTY720 acts as a functional antagonist at S1PR₁, causing internalization and degradation of this receptor and removing the lymphatic S1P gradient necessary for lymphocyte egress. As a result, this inhibits the egress of lymphocytes from lymph nodes, thereby reducing the overall number of inflammatory cells migrating to the CNS.⁵⁵ However, based on the high expression of S1PRs in the CNS, a new aspect of FTY720 function is emerging, focusing on direct neurologic cellular modulation. FTY720 has been found to easily cross the blood-brain barrier in its unphosphorylated form, where it is then phosphorylated by endogenous CNS sphingosine kinase 2.⁵³ It is then presumed that FTY720 influences the biology of CNS cells such as astrocytes and oligodendrocytes by reducing astrogliosis and demyelination.⁵⁶

The metabolism and pharmacokinetics of FTY720 have been studied both in animal studies and healthy volunteers. It has been found that FTY720 undergoes extensive metabolism, with biotransformation occurring mainly through three pathways. The first pathway is the reversible phosphorylation of fingolimod phosphate, the active metabolite, predominantly via sphingosine kinase 2, with a lesser contribution by sphingosine kinase 1. It is then dephosphorylated by lipid phosphate phosphohydrolases LPP1a and LPP3.⁵⁷ The second pathway of metabolism involves hydroxylation and oxidation via the hepatic cytochrome P450 (CYP) 4F subfamily of enzymes, which produces several inactive carboxylic acid metabolites that are then excreted in the urine.^{58, 59} CYP4 enzymes are primarily known for their role in the metabolism of endogenous fatty acids, prostaglandins, and steroids, therefore the low potential for drug-drug interactions.⁵⁸ The third pathway involves the formation of inactive non-polar ceramides.⁵⁷ In single dose studies of both fingolimod and fingolimod phosphate, it has been found that FTY720 has high oral

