bioavailability, with an absolute oral bioavailability of 93%.⁶⁰ After oral administration of a single dose, blood absolute maximum concentration is reached by 12-16 hours and found to have a long half-life of 6-9 days that is independent of drug dose.^{61, 62} Additionally, after oral administration of a single dose of fingolimod, there is a decrease in the total lymphocyte count to approximately 60% of baseline within 4-6 hours of administration and begins to recover within a few days after stopping the drug.⁶⁰

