Study Design: We propose a randomized, double-blinded, placebo-controlled pilot trial of fingolimod in patients with primary spontaneous intracerebral hemorrhage. Eligible participants will be allocated to study groups using fixed allocation randomization and a computer-based random number-generating allocation. Allocation will be equal. For those patients who meet all inclusion criteria without exclusion criteria subjects will receive oral or nasogastric tube (NGT) or Dobhoff feeding tube administration of fingolimod versus placebo. Participants will be monitored at time of enrollment and days 1, 3 5, 7, and 14 (discharge dependent) by 2 blinded assessors (neuroscience subspecialists) and will receive standard of care for the duration of the study. After discharge from the hospital, participants will enter a follow up phase of 12 months, with clinic visits at 30 ± 14 days, 90 ± 14 days, 180 ± 14 days, and 365 ± 14 days. They will receive a standard of care Neuroimaging at these follow up time-points day visit and will be assessed with the pre-selected outcome assessments established by the NINDS Common Data Elements for Stroke.

Laboratory studies: We will perform standard of care CBC with differential and flow cytometry to follow numbers of T helper cells, cytotoxic T cells, B cells, and macrophages in peripheral blood to assess the viability of these levels as a biomarker of drug effect.

Cells isolated from the peripheral blood or CSF will be incubated with a panel of antibodies to identify the following immune populations: CD4+ T cells: CD4+CD3+ and Tbet (Th1), GATA-3 (Th2), ROR \square T (Th17) FoxP3 (Treg); CD8+ T cells: CD8+CD3+T-bet; CD19+ B cells; M1:CD68+CD163-CD80+CD64+; M2:CD68+CD163+CD206+TGM2+

Additional markers of activation/differentiation tested include P2Y12, S1PR1, S1PR5, PD-1. Cells will be washed and analyzed using the BD Fortessa flow cytometric analysis instrument. In some cases, populations will be isolated for further analysis by fluorescence-based cell sorting.

With the use of commercially available assays, quantification of the top 5-10 cytokines that are present in the peripheral blood will also be performed.

We will store all CSF and blood samples to perform future Next-Gen multi-omic analysis of all CSF and blood samples including: mRNA-seq, SPLiT-seq, antibody fluorescent, DNA methylation, and mass spectroscopy. Future laboratory study procedures as detailed below.

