- **Aim 1. Safety of a single dose of fingolimod in ICH patients.** The purpose of the primary analyses will be to measure safety and feasibility of the intervention (rates of drug-related adverse events, nosocomial infections, and neurologic decline), and to measure these in the comparison group to help inform feasibility and elements of design for a future trial. In general, we will estimate composite outcome rates (95% CIs) in our study groups, for example of UTI, sepsis, and hospital-acquired pneumonia events, and we will compare these rates to historical rates, when available. This will help ensure the rates of adverse events are not elevated, and are comparable or lower than those in previous reports. Baseline demographic and clinical characteristics will be described and

compared between medical management groups, and differences may be used to help explain heterogeneity in the safety outcomes.

- **Aim 2. Evaluate CD4+ T, CD8+ T, and CD19+ B cells as biomarkers of drug effect in a critically ill ICH population.** To provide initial assessments of ‘clinical activity,’ we will compare inflammation-related biomarkers between the fingolimod and placebo groups over time. In general, we will calculate individual-level changes in the biomarkers from baseline to the later biomarker collections. For example, changes in CD4+ and CD8+ T cells and CD19+ B cells at 24 hr, 72 hr, 5-7 days, and 30 days will be useful to evaluate if levels of inflammation are lower with fingolimod. Prior to analysis, summary statistics and graphic approaches will be used to examine data distributions, both overall, and by study group. Changes will then be compared between the groups using the two-sample *t* test or Wilcoxon rank sum test and alpha level = 0.05 (two-sided). These initial assessments will be interpreted cautiously, given the small sample sizes and possible missing data.

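### Aim 2 should treat CD4+, CD8+ and CD19+ counts as markers of drug effect; an early fall cannot show whether inflammation is lower, because the drug itself holds these cells in lymph nodes

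*Combined protocol and SAP*

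**What the plan says.** Under Statistical Analysis, Aim 2 is headed as an evaluation of the three cell types as biomarkers of drug effect. To give a first look at clinical activity, the text then says "we will compare inflammation-related biomarkers between the fingolimod and placebo groups over time". Its worked example is the change from baseline in CD4+, CD8+ and CD19+ cells at 24 hr, 72 hr, 5-7 days and 30 days, which "will be useful to evaluate if levels of inflammation are lower with fingolimod". The arms are compared by two-sample t test or Wilcoxon rank sum test at a two-sided 0.05 level. The one caution given concerns small samples and possible missing data.

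Section 1.4 describes what the drug does to these cells. It says that "S1PR₁ is highly expressed on T and B lymphocytes" and that the drug acts as a functional antagonist at that receptor. It continues that "this inhibits the egress of lymphocytes from lymph nodes, thereby reducing the overall number of inflammatory cells migrating to the CNS". For a single dose it reports a "decrease in the total lymphocyte count to approximately 60% of baseline within 4-6 hours of administration", after which the count "begins to recover within a few days after stopping the drug". The half-life is given as 6-9 days.

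The Laboratory studies paragraph also plans staining for Th1, Th2, Th17 and Treg markers, and states that "quantification of the top 5-10 cytokines that are present in the peripheral blood will also be performed". The Aim 2 analysis text names neither.

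**The concern.** The heading of Aim 2 and its worked example ask different questions. Whether the counts mark drug effect can be answered with these data. Whether inflammation is lower cannot, because the drug moves the measured cells out of the blood by a route that does not require inflammation to change. An early fall shows that the drug was absorbed and engaged its receptor. It cannot separate less inflammation from no change.

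A CD4+ count also combines cells with opposing roles. Table 1 in section 1.3 lists Th1 and Th17 cells as pro-inflammatory, and Th2 and Treg cells as anti-inflammatory. Of Treg cells the protocol says: "These cells are known for their anti-inflammatory function by mediating immune tolerance to self-antigens". So the direction of a CD4+ change does not by itself indicate the direction of inflammation.

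The pilot is meant to inform a later trial. Target engagement reported as reduced inflammation would give that trial's designers an activity signal that the data do not contain.

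**Working it through.** The documents give no power, effect size or SD for Aim 2, so there is no figure of the plan's own to reproduce. Two checks were made.

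**1. How long should the drug's own effect on counts matter?**

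Inputs: half-life 6-9 days and the sampling times in Aim 2. Fraction of drug remaining = 0.5^(days / half-life).

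| Day | Half-life 6 days | Half-life 9 days |
|---|---|---|
| 1 | 0.89 | 0.93 |
| 3 | 0.71 | 0.79 |
| 5 | 0.56 | 0.68 |
| 7 | 0.45 | 0.58 |
| 30 | 0.03 | 0.10 |

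The footnote to the schedule of assessments puts the 24-hour column at least 6 hours after dosing, which is after the reported 4-6 hour fall. The drug's direct effect is therefore likely to be present at the first three sampling times, and small at 30 days.

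**2. How often would the planned test be significant from redistribution alone?**

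Inputs from the documents: total lymphocytes fall to about 60% of baseline (section 1.4); two-sided alpha 0.05 (Aim 2); equal allocation; 30 subjects with 10 open-label. The Sample Size text does not settle whether those 10 are inside the 30, so both 10 and 15 per randomised arm are shown.

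Assumptions: the total-lymphocyte fall applies to each subset; there is no mean change on placebo; inflammation is the same in both arms; the SD of the log change is 0.3 to 0.6.

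Formulas: standardised difference d = |ln(ratio)| / SD, noncentrality = d × √(n/2), with 2n − 2 degrees of freedom. The probability is taken from the noncentral t distribution.

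For a ratio of 0.6, |ln 0.6| = 0.511. With n = 10 and SD 0.3, d = 0.511/0.3 = 1.70, noncentrality = 1.70 × √5 = 3.81, critical t (18 df) = 2.101, and the probability is 0.95. All results, for one comparison at one time point:

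| Ratio to baseline | n per arm | SD 0.3 | SD 0.4 | SD 0.5 | SD 0.6 |
|---|---|---|---|---|---|
| 0.6 | 10 | 0.95 | 0.77 | 0.58 | 0.44 |
| 0.6 | 15 | 0.99 | 0.92 | 0.77 | 0.61 |
| 0.8 (partial recovery, assumed) | 10 | 0.35 | 0.22 | 0.16 | 0.12 |
| 0.9 (near recovery, assumed) | 10 | 0.12 | 0.09 | 0.07 | 0.07 |

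On the percent-change scale, a 40-point fall with an assumed SD of 15 to 50 points gives more than 0.99 down to 0.40 with 10 per arm, and more than 0.99 down to 0.56 with 15. The pattern is the same on both scales.

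In every row the counts really do differ between arms, so a significant result is a correct finding about counts. The error would lie in reading it as a finding about inflammation.

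**The case against.** The strongest reply is that most of the protocol already treats these counts as pharmacodynamic. The aim is titled that way, the Laboratory studies paragraph tests their viability as a biomarker of drug effect, and the hypothesis expects the effect seen in multiple sclerosis patients. The disputed sentence is offered as an example of something useful to evaluate. A reader might infer that the plan commits itself to declaring lower inflammation whenever the test is significant. It sets no such rule, and this part of the reply stands. The sentence nevertheless names inflammation as what the counts help to evaluate, and the stated caution about sample size and missing data does not reach the mechanism.

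Second, section 1.4 presents retention in lymph nodes as the route by which fewer inflammatory cells reach the brain. That also stands: a fall in counts is not unrelated to CNS inflammation, and redistribution with no change in inflammation is an assumption made here for illustration. But a proposed pathway makes the result compatible with benefit without demonstrating it. The same section cites a rodent ICH study in which edema fell with no difference in inflammatory cell numbers.

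Third, the plan separately correlates biomarkers with perihematomal edema under Aim 3. This is useful, but it is exploratory and does not condition how the Aim 2 result is read.

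Fourth, the figures rest on a 4-6 hour fall in total lymphocytes, on assumed SDs and on an unsettled arm size. The listed secondary outcome for the subsets is at 30 days, where the effect should be weakest. All of this is correct, and it is why the figures are only illustrative.

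**Conclusion.** The point holds for the inference and not for the measurement. The subset counts are reasonable markers of drug effect. At 24 hr, 72 hr and 5-7 days they cannot indicate whether inflammation is lower, since the protocol's own pharmacology predicts a fall either way. At 30 days the objection is weaker.

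If the 60% figure carries over to the subsets, a significant result without any change in inflammation has probability 0.44 to 0.95 (10 per arm) or 0.61 to 0.99 (15 per arm) over the assumed SDs. With recovery to 80-90% of baseline it is 0.07 to 0.35 (10 per arm).

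Three stronger readings are tempting and unsupported:

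- A reader might set these probabilities against the nominal 0.05 and call them an inflated false-positive rate. They are power for a true difference in counts.
- A reader might infer that a positive result is close to automatic. That fits only low variability at early visits.
- A reader might infer that the plan excludes cytokines and T-cell subtypes from Aim 2, or would score loss of Treg cells as benefit. The cytokines and subtypes are unnamed in Aim 2 rather than ruled out, and nothing in the text scores Treg loss.

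**What to change.** In Statistical Analysis, Aim 2:

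1. Describe the CD4+, CD8+ and CD19+ comparison as a pharmacodynamic (target-engagement) analysis, in line with the aim's title. Delete the statement that it evaluates whether inflammation is lower.
2. Base any statement on inflammation on a between-arm comparison of markers that are already planned and are not set directly by lymphocyte egress: the blood cytokines in Laboratory studies and perihematomal edema volume. Fix the cytokine list before unblinding, because the present wording leaves the choice of 5-10 open. Label these comparisons exploratory. Table 1 should not simply be adopted as the list. The protocol does not say that those cytokines are assayed, and section 1.3b places IL-6 among the Th2 cytokines and TGF-β among those of Th17, which does not match the directions in Table 1.
3. Th1, Th2, Th17 and Treg fractions of CD4+ may be reported descriptively, with a note that egress can affect these fractions too.

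The cost is protocol wording, a decision on the cytokine list and a little extra analysis of measurements already planned. The downside is a more modest claim for Aim 2.
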